6.4 Follow-Up Phase

The schedule of assessments and procedures to be performed during the Follow-up Phase are outlined below by Study Day and in the “Study Schedule of Events” (see Table 1).

6.4.1 Day 21

Patients will undergo the following procedures on Day 21.

1. Abbreviated physical examination;
2. Vital signs including sitting blood pressure, pulse rate, respiratory, and temperature after sitting for 3-5 minutes;
3. Collection of clinical laboratory samples (blood and urine) to be shipped to the central lab for evaluation of hematology, blood chemistry, coagulation parameters and urinalysis;
4. Collection of blood samples for hsCRP and D-dimer assessments;
5. For patients randomized to the SelK2 arm or SelK2 + enoxaparin arm, collection of blood samples for PK, PD, and immunogenicity assessments;
6. Record concomitant medications and transfusion; and
7. Assessment of AEs.

6.4.2 Day 29

Phone contact to assess the following:

1. Record concomitant medications and transfusions; and
2. Assessment of AEs.

6.4.3 Day 43

Phone contact to assess the following:

1. Record concomitant medications and transfusions; and
2. Assessment of AEs.

6.4.4 Day 57

Patients will undergo the following procedures on Day 57.

1. Complete physical examination;
2. 12-lead ECG;
3. Vital signs including sitting blood pressure, pulse rate, respiratory, and temperature after sitting for 3-5 minutes;
4. Collection of clinical laboratory samples (blood and urine) to be shipped to the central lab for evaluation of hematology, blood chemistry, coagulation parameters and urinalysis;
5. Collection of blood samples for hsCRP and D-dimer assessments;

6. For patients randomized to the SelK2 arm or SelK2 + enoxaparin arm, collection of blood samples for PK, PD, and immunogenicity assessments;
7. Record concomitant medications and transfusions; and
8. Assessment of AEs.

The completion of assessments listed above on Day 57 marks the completion of each patient in this study.

Patients should be reminded that they must remain on a highly effective contraceptive method until 30 days after their Final Study Visit.

6.4.5 Early Discontinuation Visit

IMPORTANT NOTE: For patients that are early terminating from the study, site personnel should make every effort to have patients undergo an Early Discontinuation Visit which has assessments identical to those done for the final safety visit on Day 57.

Patients will undergo the following procedures at their Early Discontinuation Visit

1. Complete physical examination;
2. 12-lead ECG;
3. Vital signs including sitting blood pressure, pulse rate, respiratory, and temperature after sitting for 3-5 minutes;
4. Collection of clinical laboratory samples (blood and urine) to be shipped to the central lab for evaluation of hematology, blood chemistry, coagulation parameters and urinalysis;
5. Collection of blood samples for hsCRP and D-dimer assessments;
6. For patients randomized to the SelK2 arm or SelK2 + enoxaparin arm, collection of blood samples for PK, PD, and immunogenicity assessments;
7. Record concomitant medications; and
8. Assessment of AEs.

6.5 Measurements and Assessments

Details of specific efficacy, safety, PK, and PD assessments are provided in this section. Additional details are provided in the Laboratory Manual.

6.5.1 Efficacy Assessments

6.5.1.1 Venography

A unilateral ascending venogram of the operated leg is to be performed for each study patient between Day 9 and Day 13 of the study, approximately 10 days after completion of TKA. The Manual for Venography and Event Reporting describes instructions for the venography and image acquisition. A venography will be evaluable when images with multiple views of all the deep veins of the leg can be evaluated (only exception is the deep femoral vein which sometimes difficult to visualize).

6.5.1.2 Suspected Symptomatic VTE

Patients will be evaluated for signs and symptoms of DVT (e.g., swelling, localized pain, redness, heat, localized warmth) and PE (e.g., unexplained shortness of breath, coughing up blood, chest pain that gets worse with a deep breath, unexplained coughing) during the post-surgery in hospital/clinic period and at all visits occurring throughout the Treatment and Follow-up Phases of the study. Patients with suspected DVT and or PE should undergo further diagnostic testing per hospital routine (e.g compression ultrasound for suspected DVT and spiral CT scan for patients with PE). Every suspected episode of DVT or PE must be reported appropriately as an AE and the underlying supportive data (e.g images and reports of diagnostic tests, hospital reports) will be submitted for adjudication by the CIAC. The Study Site Manual for Venography and Event Reporting provides instruction on the documentation, data collection, and reporting required for each suspected episode of DVT or PE.

If patients would have a PE or DVT confirmed by diagnostic testing during the Treatment Phase, the planned venography of the operated leg is not required.

If a patient would have an event that requires therapeutic anticoagulant treatment, the prophylactic dosing of enoxaparin will need to be discontinued. The anticoagulant treatment undertaken will be at the discretion of the treating physician and any question regarding SelK2 should be referred to the medical monitor by contacting the medical help line.

6.5.1.3 Laboratory Markers of Inflammation and Thrombosis

Blood sampling will be collected on Screening, Day 1, Day 4, Day 6 (optional), Day 11, Day 21, and Day 57 for assessment of hsCRP and D-dimer.

6.5.1.4 Pharmacokinetic and Pharmacodynamic Assessments of SelK2

Blood sampling will be performed to supply 2 mL of serum for PK evaluations and 2 mL of serum for PD evaluations in patients randomized to SelK2 arm or adaptive arm. Blood samples will be collected via an indwelling catheter and/or via direct venipuncture. Please note that since the PK and PD samples will generally be collected at the same time points, one tube will be used to collect both samples and then samples aliquoted accordingly.

Blood sampling will be collected on Day 1 (pre-dose SelK2), Day 2 (prior to TKA), Day 4, Day 6 (optional), Day 11, Day 21, and Day 57 for assessment of PK and PD.

The exact date and sampling time will be recorded on the appropriate eCRF page. Please refer to the Laboratory Manual for details of collection, storage, and shipping of samples.

The PK and PD assays will be performed at Cytovance Biologics, [name].

6.5.2 Safety Assessments

Safety assessments for this study include the following:

6.5.2.1 Adverse Events

Adverse events will be assessed by standard non-leading questions. All clinical AEs occurring from Randomization on Day 1 and up until the Day 57 visit whether observed by the investigator or reported by the patient will be assessed, documented, and reported in accordance with ICH GCP guidelines. Section 7.0 outlines the definitions, collection periods, criteria, and procedures for documenting, grading, and reporting AEs. A separate document that details AE eCRF completion guidelines for Investigators as well as training will be provided.

6.5.2.1.1 *Bleeding*

All suspected bleeding events are to be reported and additional examination will be done if deemed necessary by the investigator depending on the type of bleeding (e.g. hematology blood sample, endoscopy). If a patient has a hemorrhagic stroke both stroke and bleeding will be reviewed.

Narratives of bleeding events should be detailed and contain the following elements at the minimum:

- Location of the bleeding
- Size (in case of hematoma)
- Duration
- Provocation e.g. associated with any procedure
- Hemoglobin values prior and after bleeding if available
- Any transfusion or medication given

Other bleeding related parameters should be recorded during the trial:

- Hb level, HCT and red cell count changes during the treatment period
- Blood loss (peri-, post-operative) quantified by the routine method in each hospital
- Number of transfusions of packed red cells and transfused quantities until follow-up (e.g., 30 days after surgery; homologous and autologous transfusions need to be distinguished)

If a decrease in hemoglobin, blood loss or more transfusions are given than expected following TKA a suspect bleeding event needs to be reported and the narrative as specified above needs to be completed.

The data of all reported bleeding events or potential bleeding event must be submitted to the CIAC. The Study Site Manual for Venography and Event Reporting provides instruction for sites on the documentation, data collection, and reporting required for each suspected bleeding event.

Approach to Patients With Acute Bleeding

The following steps are recommended for patients with ongoing life-threatening bleeding (bleeding resulting in hemodynamic compromise requiring intervention or any intracranial hemorrhage):

- Withhold enoxaparin and all other anticoagulant/antiplatelets;
- Institute standard of care for life-threatening bleeding (large bore IV or central venous line, type and crossmatch blood, admit to the intensive care unit, provide hemodynamic and respiratory support);
- Administer antidotes if applicable (e.g., administer protamine if the patient had recently received heparin); and
- Administer packed red blood cells (or whole blood) as needed.

Use of prothrombin complex concentrates (PCCs), recombinant Factor VIIa, other factor procoagulants, or antifibrinolitics (depending upon the clinical situation and local availability) should be considered in consultation with a local available hematology expert. The SelK2 Medical Support Line ([contact]) can be contacted to discuss patient management (English language only).

6.5.2.1.2 *Stroke*

If a patient has a suspected stroke, the diagnostic work-up should be performed according to the hospital routine (it is expected that CT scans/MRI of the brain are done). Stroke will be reviewed by the CIAC to evaluate whether hemorrhagic stroke was present which will be considered as a major bleeding event.

6.5.2.1.3 *Death*

For patients who died, the adjudication committee will need to classify cause of death and will attribute death to PE if no other cause can be identified.

It is therefore crucial to provide a detailed description including the sequence of events preceding death (e.g. “patient gradually deteriorated and was found dead, or patient became suddenly short of breath and collapsed”).

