3.6.5 Safety Endpoints

Safety parameters for this study include the following:

- Bleeding Events
- Other Adverse Events
- Clinical laboratory measurements
- Additional laboratory evaluations
- Physical examination and vital signs
- 12-lead ECGs
- Immunogenicity (anti-SelK2 antibodies) assessment
- Transfusion(s) with blood products
- Pregnancy test

Suspected bleeding events will be adjudicated in a blinded fashion for categorization as a:

- 1) Major Bleeding event (MB),
- 2) Clinically Relevant Non-Major Bleeding event (CRNMB),
- 3) Minor Bleeding, or
- 4) No Bleed.

The criteria for classification are specified in the CIAC charter and will include the classification for major bleeding in the surgical setting (8).

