5.1.2 Blinding, Packaging, and Labeling of Study Drug

This is a randomized and unblinded study, consequently no effort is required to blind study drug or active comparator from any of the study personnel at the clinical site. A pharmacist will be responsible for the compounding of individual doses of study drug (SelK2) for patients randomized to receive SelK2.

Each SelK2 vial is labeled in accordance with specific country regulatory requirements as well as with the study number, specific drug contents, and unique vial number.

Enoxaparin pre-filled syringes will be labeled in accordance with specific country regulatory requirements.

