7.2.1 Reporting Requirements for AE's that are Potential Study Endpoints

The Study Site Manual for Venography and Event Reporting provides instruction for sites on the documentation, data collection, and reporting required for events considered (suspected) endpoints.

Typically for the above clinical events of suspected symptomatic DVT, suspected symptomatic PE, bleeding, stroke, or death, data will be collected in order to generate an adjudication dossier which will consist of eCRF data and supportive documentation which is assembled for review by the CIAC.

All suspected clinical outcomes must be reported as adverse events. Reporting a suspected outcome as an adverse event on the AE page in eCRF will automatically trigger an event specific form (refer also to eCRF completion guidelines). The eCRF triggered event forms contain a narrative section. In this narrative, a short clinical description should be provided: e.g. including symptom description and duration, eventually performed diagnostic tests or intervention with dates and description.

The supportive documentation (adjudication dossier) will depend on the type of clinical event and will typically consist of images and reports of the diagnostic tests done to explore the suspected clinical event, and other reports that could be relevant to the CIAC (e.g. medical records and/or hospital letters, discharge summaries, laboratory tests).

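### Whether a perioperative hemoglobin fall, blood loss or transfusion goes to blinded bleeding adjudication rests on an undefined judgement by unblinded sites, with no treatment-independent route

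*Combined protocol and SAP*

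**What the plan says.** **Who knows the treatment.** Section 5.1.2 states "This is a randomized and unblinded study" and adds that "no effort is required to blind study drug or active comparator from any of the study personnel at the clinical site".

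**How a bleed is raised.** Section 6.5.2.1.1 opens with a general duty: "All suspected bleeding events are to be reported and additional examination will be done if deemed necessary by the investigator". It then adds a rule for the surgical setting: "If a decrease in hemoglobin, blood loss or more transfusions are given than expected following TKA a suspect bleeding event needs to be reported". No hemoglobin change, volume or number of units is given.

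**How it reaches the committee.** "The data of all reported bleeding events or potential bleeding event must be submitted to the CIAC" (6.5.2.1.1). Under 7.2.1 the site's own entry starts the process: "Reporting a suspected outcome as an adverse event on the AE page in eCRF will automatically trigger an event specific form". The CIAC reviews each suspected bleed blinded (3.5, 11.4) and may class it as major, clinically relevant non-major, minor or no bleed (3.6.5).

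**How the result is used.** The primary safety outcome is major or clinically relevant non-major bleeding in the Treatment Phase (Synopsis, Safety; 1.4). Section 10.4 tabulates bleeding as adjudicated. Section 10.5 gives the same tables to the Steering and Safety Committee, which also advises on opening the combination arm.

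**What else is recorded.** Hematology is run centrally, with Treatment Phase samples on Days 1, 4 and 11 (Table 1, 6.5.2.2). Transfusions are recorded at every visit. Section 6.5.2.1.1 also asks for "Blood loss (peri-, post-operative) quantified by the routine method in each hospital". The safety parameters in 3.6.5 include "Transfusion(s) with blood products".

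**The concern.** Some blood loss, some fall in hemoglobin and some transfusion are ordinary after knee replacement. Whether a given amount is unusual is a matter of opinion, and here the opinion is formed by someone who knows which drug was given. The Introduction (1.1) presents currently available agents as causing major bleeding and selectin inhibition as acting without it, so site staff may hold different expectations for the two arms.

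Blinded adjudication protects the classification of the events it receives. It does not protect the step before, where a patient does or does not become an event. The main efficacy component has no such gap, because every scheduled venogram goes to the CIAC whatever the site thinks.

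At stake is the between-arm comparison of the primary safety outcome, and a safety input to the decision on the combination arm.

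**Working it through.** **1. Tracing the routes to the CIAC.**

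| Route | Section | Who starts it | Needs a site judgement? |
|---|---|---|---|
| Any suspected bleed | 6.5.2.1.1, first sentence | Site | Yes: is bleeding suspected? |
| Hemoglobin fall, blood loss, transfusion | 6.5.2.1.1, quoted rule | Site | Yes: is it beyond what was expected? |
| Abnormal laboratory value | 6.5.2.2 | Site, as an adverse event | Yes: is it clinically significant? |
| Suspected stroke, death | 6.5.2.1.2, 6.5.2.1.3, 7.2 | Site | Little for death; some for stroke |

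No section sends hemoglobin, transfusion or blood-loss data to the CIAC for a patient without a reported event.

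**2. Reading the quoted rule.** The comparison with expectation may qualify all three items or only transfusions. On the narrower reading, any hemoglobin decrease or blood loss after surgery would be reportable. Sites could apply either reading, so the sentence needs rewording in any case.

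**3. Plan figures.** The documents give no bleeding rate, margin or power, so there is no bleeding figure to reproduce. The only plan number used below is 95 patients per arm, from 10.1. It reproduces: (1.2816 + 0.8416)² × 2 × 0.25 × 0.75 / 0.15² = 75.1, rounded up to 76 evaluable; 76 / (1 − 0.20) = 95.

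**4. Illustration (all rates assumed).** Let p be the true rate, equal in both arms; f the share of events that depend on the quoted rule; and s the probability that the site reports such an event. All other events are taken as reported.

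Observed rate = p(1 − f) + p·f·s

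Take p = 10%, f = 80% and s = 90% on enoxaparin:
- Enoxaparin: 0.10 × 0.20 + 0.10 × 0.80 × 0.90 = 9.2%, about 8.7 of 95.
- SelK2, s = 70%: 0.020 + 0.056 = 7.6%, about 7.2 of 95; ratio 0.83.
- SelK2, s = 50%: 0.020 + 0.040 = 6.0%, 5.7 of 95; ratio 0.65.

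The ratio (1 − f + f·s₁)/(1 − f + f·s₂) does not depend on p. For f from 50% to 100%:

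| Reported, SelK2 vs enoxaparin | False ratio |
|---|---|
| 70% vs 90% | 0.89 to 0.78 |
| 50% vs 90% | 0.79 to 0.56 |
| 90% vs 70% | 1.12 to 1.29 |
| 60% vs 60% | 1.00 (both rates too low) |

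In patients, with p from 5% to 15%, the gap in the first two rows runs from about 0.5 of 95 (a 0.5-point difference) to 5.7 of 95 (a 6-point difference).

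**5. Cross-check outputs.** Section 10.4.2 summarizes hematology by arm, with change from baseline. Transfusion and blood loss are named neither in 10.4 nor in the committee list in 10.5.

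**The case against.** The strongest reply is that the protocol already casts a wide net. The duty to report all suspected bleeding is unconditional, so the quoted rule adds to it. A dossier is required even when local tests do not confirm the event (7.2). Hemoglobin will be compared by arm whatever sites report (10.4.2). The Steering and Safety Committee sees laboratory values beside adjudicated bleeds (10.5), and the academic research organization reviews accumulating safety data and manages endpoint collection (11.2). The site manual, the adverse event completion guidelines and the CIAC charter were not supplied and may contain thresholds.

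Most of this stands, and it rules out two stronger readings.

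- A reader might infer that a surgical bleed reaches the CIAC only if the site finds it beyond expectation. The text does not support this: an overt bleed such as a hematoma is reportable under the general duty.
- A reader might infer that the bias favors SelK2. Background statements make that plausible, but sites could equally be more watchful with a new antibody. No passage settles the direction.

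The safeguards do not close the gap. Suspicion is also an unblinded judgement. The dossier rule in 7.2 applies once an event has been suspected. By-arm laboratory summaries may reveal a mismatch with reported bleeds, but they refer no patient for adjudication.

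**Conclusion.** The point holds in limited form. In the supplied text, referral of a perioperative hemoglobin fall, blood loss or transfusion turns on an undefined judgement by unblinded sites, and no treatment-independent route to the CIAC exists. Over-reporting can be corrected by adjudication; non-reporting cannot. The primary safety outcome is therefore open to differential ascertainment in either direction.

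The size is unknown. The ratios above rest on assumed true rates, trigger shares and reporting probabilities, and on 95 treated patients per arm; they show what is possible and estimate nothing. The shift would be at most a few patients per arm, but the safety analysis is descriptive (10.4), so such a shift would pass straight into the reported rates. If the site manual or charter already holds numeric thresholds, the lack of a definition falls away, but the dependence on a site report remains unless those documents also provide for automatic referral.

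This is a worthwhile design improvement, not a demonstrated error in the plan.

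**What to change.** **Section 6.5.2.1.1.** Add a central programmed query, identical in all arms. It refers a patient to the CIAC when the fall in central-laboratory hemoglobin from Day 1 (scheduled Days 4 and 11), or the recorded red-cell units, meet the numeric criteria in the CIAC charter, whether or not the site reports a bleed. If the charter has no numeric criteria, fix thresholds in advance. Day 1 is a sound baseline because Table 1 places that sample before randomization. Keep site reporting for all other suspected bleeds, and reword the quoted sentence so that its scope is clear.

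**Sections 10.4 and 10.5.** Add by arm the proportion transfused, the units transfused and measured blood loss. Compare blood loss within site, since hospitals use their own methods. Read these beside the hemoglobin changes already planned in 10.4.2, as a cross-check on adjudicated bleeding.

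**Cost and limits.** The data are already collected. The work is a short protocol change, a query, a few tables and matching edits to the site manual and possibly the charter. The CIAC will see more dossiers, many of which it will class as no bleed. Scheduled samples can miss a low on Day 2 or 3, and a transfusion can mask a fall. Unblinded staff decide on transfusion, so red-cell units are not fully independent of arm, and hemoglobin is the more objective trigger.

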6.5.2.2 Clinical laboratory measurements

Blood (for hematology/CBC and clinical chemistry panel) and urine samples (for urinalysis) will be collected according to the Study Schedule of Events and analyzed at a central laboratory. All blood samples will be collected while patients are in a seated or supine position. Specific instructions for the collection, processing, and shipment of samples will be provided in the Laboratory Manual. Laboratory test results that are abnormal and considered clinically significant must be reported as AEs. Screening laboratory results must be available before randomization.

All of the major clinical laboratory assessments (including Clinical Chemistries, Hematology/CBC, complete Urinalysis (UA), coagulation parameters (PT/INR and aPTT) will be conducted at the central laboratory. In addition, at screening, samples for HIV (HIV antibody), Hepatitis B (HBsAg), Hepatitis C (Anti-HCV antibody) and serum pregnancy (women only) will be collected for analysis at central laboratory. All supplies for clinical laboratory sample collection will be provided in the form of kits from the central laboratory.

The samples for laboratory assays and the visits at which these samples will be collected are indicated in Table 1 (Study Procedures Schedule of Events).

Table 2 provides an exhaustive and complete listing of all the clinical laboratory assessments that will be included in this study.

Table 2. Listing of All Clinical Laboratory Assays Included in Clinical Chemistry, Hematology (CMC), Complete UA and Coagulation Parameters

Chemistry:	Hematology (CBC):	Complete UA:
Albumin	Hematocrit	pH and Specific Gravity
Alkaline Phosphatase	Hemoglobin	Glucose
Alanine Transaminase (ALT)	MCH	Protein
Aspartate Transaminase (AST)	MCHC	Blood
Blood urea nitrogen (BUN)	MCV	Ketones
Calcium	MPV	Reflexive Microscopic analysis (including RBCs and WBCs per high power field)
Chloride	Platelet count	
Bicarbonate/Carbon Dioxide (CO ₂)	Red blood cell distribution width (RDW)	Coagulation Parameters:
Creatinine	Red blood cell (RBC) count	Prothrombin Time/International Normalized Ratio (PT/INR)
Direct Bilirubin	White blood cell (WBC) count	activated Partial Thromboplastin Time (aPTT)
Gamma glutamyl transferase (GGT)	White blood cell differential	
Glucose	(% & Absolute):	
Lactate Dehydrogenase (LDH)	Basophils	
Phosphorus	Eosinophils	
Potassium	Lymphocytes	
Sodium	Monocytes	
Total Bilirubin	Neutrophils	
Total Protein		
Uric acid		

